Overall trial design	week period (i.e., subjects must have IGA of 2 and not achieve EASI75 at 3	becoming ≥ 2 ; IGA of 1 becoming
Appendix 1	consecutive visits).	≥ 3).
Protocol summary	(ii) On a single occasion, an IGA of at	
	least 3 and not achieving EASI75.	
	(iii) On a single occasion not	
	achieving EASI50 with an IGA of at	
	least 2.	
	Subjects with IGA=0 at Week 16:	
	IGA of at least 2 and not achieving EASI75 over at least a 4-week	
	period (i.e., over 3 consecutive	
	visits).	
	Subjects with IGA=1 at Week 16:	
	IGA of at least 3 and not achieving	
	EASI75 over at least a 4-week	
	period (i.e., over 3 consecutive	
	visits).	
	Subjects with IGA >1 at Week 16:	
	Not achieving EASI75 over at least	
	a 4-week period (i.e., over	
	3 consecutive visits).	
Section 4	All subjects must use an emollient	Clarification that the use of
Schedule of	twice daily (or more, as needed)	background treatment (emollients)
procedures		is at least twice daily or more, as
Section 7.1		needed. This change has been
Overall trial design		implemented throughout the document.
Section 8.2		
Inclusion criteria		
Section 9.4		
Background		
treatment		
(emollients)		
Appendix 1		
Protocol summary		

Trial	ID:	LP01	62-1325

Section number and name	Description of change	Brief rationale
Section 4	The following text has been added to	Specification that the 2 screening
Schedule of	footnote no. 1 in Panel 2:	visits (visits 1 and 2) will be
procedures	Similarly, for subjects who only	combined for subjects who only
Section 7.1	require a 2-week wash out,	require a 2-week wash-out.
	screening visits 1 and 2 will be	
Overall trial design	combined (Week -2).	
	In Section 7.1, the following text has	
	been added under Screening period:	
	Similarly, if only a 2-week wash-out	
	is required, screening visits 1 and 2	
0 4 51	will be combined (Week -2; visit 2).	
Section 5.1	Treatment recommendations for AD	Corrections as no toxicities have
Atopic dermatitis	include topical therapies, the main	been reported with long-term
	being topical corticosteroids (TCS).	treatment with TCIs.
	Unfortunately, TCS and topical	
	calcineurin inhibitors (TCIs) have	
	limited efficacy in patients with moderate to severe disease. TCS and	
	non-biologic other treatment options	
	like topical calcineurin inhibitors	
	(TCI) and systemic therapies are all	
	associated with toxicities with long-	
	term use (6-8).	
Section 5.5	A number of theoretical potential	Infusion reactions have been
Benefit/risk	risks have been identified that are	deleted from the list since they are
assessment	described in the current Investigator's	not relevant for this trial.
	Brochure, including hypersensitivity	Malignancies and interference
	reactions, infusion reactions, immune	with reproductive function added
	complex disease, and severe	to align with the Investigator's
	infections, malignancies, and	Brochure.
	interference with reproductive	
	function	
Section 8.3	10. Receipt of any marketed (i.e.	Dupilumab is now approved in
Exclusion criteria	immunoglobulin, anti-IgE) or	USA, and has therefore been
	investigational biologic agent,	added to exclusion criterion no.
	including dupilumab	10.
	18. History of anaphylaxis following	Clarification on which kind of
	any biologic therapy.	previous anaphylaxis will lead to
		exclusion. A large proportion of
		subjects with moderate to severe
		AD will have had food allergies
		and other allergies during
		childhood, manifested as
		anaphylaxis, with no relevance for
		later risk of anaphylactic reactions
		to tralokinumab.

Section number and	Description of change	Brief rationale
name		
Section 8.5	Subjects who permanently	Clarification that subjects who
Discontinuation	discontinue treatment IMP for any	permanently discontinue IMP
Section 4	reason will be asked to attend an	prior to Week 16 should also be
Schedule of	early termination visit and return	assessed at the nominal Week 16
procedures	to the trial site for 1 or 2 additional	visit. This will allow sensitivity
1	visits as indicated below depending	analyses of primary endpoints and
	on the time of discontinuation of	secondary endpoints in the initial
	IMP should attend an early	treatment period.
	termination visit and a safety follow-	
	up visit 16 weeks after last	
	administration of IMP (see the SoP	
	[Section 4] for data to be collected at	
	these visits). The investigator will	
	review any AEs which will be	
	followed up according to	
	Section 11.6, if the subject agrees.	
	Subjects who permanently	
	discontinue IMP prior to Week 16	
	will be asked to attend:	
	• Early termination visit.	
	Nominal Week 16 visit	
	(16 weeks after	
	randomisation).	
	• Safety follow-up visit (16 weeks	
	after last administration of	
	Subjects who discontinue IMP at	
	Week 16 or after Week 16 will be	
	asked to attend:	
	• Early termination visit.	
	• Safety follow-up visit (16 weeks	
	after last administration of	
	IMP).	
	If a subject withdraws from the trial,	
	he/she may request destruction of any	
	samples taken and not tested, and the	
	investigator must document this in the	
	site's trial records.	
	Reason(s) for discontinuation from	
	IMP and withdrawal from the trial	
	must be recorded in the medical	
	records	

Section number and	Description of change	Brief rationale
name		
Section 9.3.2 Emergency unblinding of individual subject treatment	An emergency unblinding request can be made by the investigators, other HCPs who are not members of the trial staff, or authorised LEO personnel. Provisions are in place for 24-hour emergency unblinding of individual subject treatment. If emergency unblinding is required, the requester investigator can unblind a subject's treatment in the IWRS. For a requester who is not a member of the trial staff and who does not without have access to the IWRS (e.g., an HCP not involved in the trial a physician at an emergency room), a local contact number for the emergency unblinding CRO is provided on the subject card (see Appendix 4B) to be used if the investigator or delegated site staff cannot be reached.	Clarification regarding the procedure for emergency unblinding of the individual subject's treatment.
	Emergency unblinding CRO	Clarification throughout the section that the unblinding CRO is to be used for emergency unblinding only.
Section 9.11 Reporting product	Any defects or issues with the IMP as well as any device deficiency	Clarification that product complaints related to the IMP
complaints Appendix 7 Country-specific requirements (Japan)	(including malfunctions, use errors, and inadequate labelling) must be reported to Global Pharmacovigilance, LEO on the trial-specific (paper) Device Complaint Form within 3 days of first knowledge. Critical complaints (defined as any issue, defect, or device deficiency that has or potentially could have a serious impact for the subject [e.g., SAE or large particles in the syringe]) must be reported to Global Pharmacovigilance, LEO within 24 hours.	itself must also be reported as product complaints. Clarification that any device deficiency must be reported as a product complaint. Clarification that critical complaints are subject to expedited reporting. Clarification that adverse events in connection with product complaints are to be reported as adverse events or serious adverse events as appropriate.

Trial ID: LP0162-1325	Date: 14-Aug-2018	Version: 4.0
		Page 165 of 169

Section number and name	Description of change	Brief rationale
	This report Complaint forms should contain a detailed description of the defect, issue, or malfunction device deficiency, including whether it the malfunction led to an AE. (S)AEs which occur due to a defect or issue with the IMP or due to a device deficiency will be reported by the investigator as described in Sections 11.2 and 11.3.	
Section 10.1 Overview	Investigator assessments (performed only by adequately trained investigators; the same investigator should perform all the evaluations for a given subject throughout the entire trial period) in the following order: 1. SCORAD component C, then component A and B. 2. IGA. 3. EASI.	Clarification that SCORAD component C (completed by the subject) will be completed prior to any investigator assessments.
Section 10.3.1.1 Investigator's Global Assessment	Clinical signs and morphological descriptors have been added to the IGA scale in Panel 10.	Added following a request from the FDA.
Section 10.3.1.2 Eczema Area and Severity Index	Footnote added to Panel 12 on the EASI severity score scale: Half-points (0.5; 1.5; 2.5) may also be used.	Clarification that the EASI severity score scale also includes half-points (in alignment with the eCRF and the trial manual).
Sections 10.3.2.1 Eczema related Sleep numeric rating scale to 10.3.2.12 Treatment Satisfaction Questionnaire for Medicine	All 12 questionnaires are provided in the investigator trial file and not in a trial manual.	Clarification on where questionnaires are filed.
Section 10.4.5 Laboratory testing	The central laboratory will provide results in conventional units to trial sites in the US and in SI units to trial sites in Europe and Asia; the trial sites in the units preferred by the trial sites while the results that are transferred to the trial database will always be in conventional and SI units.	Clarification regarding the units of the results from the clinical laboratory assessments provided to the trial sites across regions. Clarification that results transferred to the trial database will be in both conventional and SI units.

Trial ID: LP0162-1325	Date: 14-Aug-2018	Version: 4.0
		Page 166 of 169

Section number and	Description of change	Brief rationale
name		
Section 10.4.7	Samples will be retained for as long	Clarification regarding storage of
Anti-drug antibodies	as the quality of the material	ADA samples.
measurements	permits evaluation but for no	
	longer than 15 years after	
	marketing authorisation.	
Section 10.5.1.2	To minimise the variation between	The RNA-based method is more
Staphylococcus	trial sites, a traditional culture based	reliable than the culture-based
aureus colonisation	non quantitative method for	method when swabs have been
	determining S. aureus colonisation	frozen.
	will be determined usedusing an	
	RNA-based method (quantitative	
	real-time polymerase chain	
	reaction).	
Section 10.6	Total volume of blood to be	2 blood samples (PK and anti-drug
Estimate of total	withdrawn has been changed from	antibodies) have been added at
blood volume	420 mL to 435 mL	Week 4
collected		
Section 11.4.1	Pregnant subjects must permanently	Alignment between Sections 9.8.1
Pregnancy	discontinue from the trial-IMP (see	and 11.4.1.
	Section 9.8.1).	

Section number and name	Description of change	Brief rationale
Section 11.5.1 Adverse events of special interest	Malignancies diagnosed after randomisation, excluding basal cell carcinoma, localised squamous cell carcinoma of the skin, and carcinoma in situ of the cervix	Basal cell carcinoma, localised squamous cell carcinoma of the skin, and carcinoma in situ of the cervix will be reported on standard AE forms as no additional information (e.g., histology report, oncology assessment, treatments) regarding these conditions need to be reported.
	Conjunctivitis, keratoconjunctivitis, and keratitis added as adverse events of special interest. The additional information about these events that the investigators will provide to LEO is also included in Panel 14.	These event types are common in the target population and should be monitored closely as per request from the authorities.
Section 11.7 Handling of an urgent safety measure	LEO must act immediately upon receipt of the urgent safety measure notification in accordance with the internal procedures and local legislation .	Clarification that the handling of urgent safety measures will be in accordance with local legislation.
Section 12.3.6.1 Analysis of maintenance endpoints	The pooled analyses will only be presented in marketing authorisation applications	Clarification that the pooled analyses of data from LP0162-1325 and LP0162-1326 will be presented in marketing authorisation applications.
Section 12.3.7.1 Adverse events	An overall summary of the number of treatment-emergent AEs, number (percentage) of subjects with any treatment-emergent AEs, SAEs, deaths, premature discontinuations from the trial due to AEs, treatment- related AEs and severe AEs will be presented.	Number of treatment-emergent AEs and deaths added to comply with ClinicalTrials.gov reporting requirements.

Trial ID	: LP0162-1325

Section number and	Description of change	Brief rationale
name	The second se	
name Appendix 4 B Informed consent process	At screening, subjects will be provided with a card stating that they are participating in a clinical trial and which contains contact address(es) and telephone number(s) of relevant trial site staff including the number for the investigator in case of emergency situations. The subject card also includes a local telephone number for the emergency unblinding CRO to be used if the investigator or delegated site staff cannot be reached or if unblinding	Clarification that the subject card also includes emergency numbers for emergency unblinding by the investigator and the emergency unblinding CRO (as also clarified in Section 9.3.2).
	in the IWRS cannot be performed.	
Appendix 4D Record keeping, quality control, and data handling	Protocol deviations will be documented and notified to the investigator. LEO will assess all protocol deviations and decide if any of these deviations must be reported to the regulatory authorities as a serious breach of GCP and the protocol, as required by local legislation. Protocol deviations will be included in the CTR. Protocol deviations will be assessed by LEO and included in the CTR.	Clarification that it will be evaluated whether protocol deviations (non-compliances) must be reported to the regulatory authorities as a serious breach of GCP and the protocol.
Appendix 8 Contact list	Update of the protocol authors.	Due to change in the responsibilities of the sponsor's personnel.
	Emergency unblinding CRO Microbiology	The name and address for the emergency unblinding CRO has been added. The name and address for the laboratory responsible for analysing skin swab data has been
	Biomarkers	added. The name and address for the 2 laboratories responsible for serum biomarker analysis has been added.
	Skin biopsies	The name and address for the laboratory responsible for gene expression analysis has been added.

Trial ID: LP0162-1325 Date: 14-Aug-2018		Version: 4.0
		Page 169 of 169

# 2 Statistical Analysis Plan Statements

# 2.1 Compliance with Good Clinical Practice

This Statistical Analysis Plan is designed to comply with the standards issued by the International Council for Harmonisation of Technical Requirements for Pharmaceuticals for Human Use (ICH) (E3: Structure and Content of Clinical Study Reports, E6: Good Clinical Practice, and E9: Statistical Principles for Clinical Trials).

Trial ID: LP0162-1325	Date: 20-May-2019	Version: 1.0
		Page 4 of 31

# 3 List of Abbreviations

# 3.1 List of Abbreviations

AD	atopic dermatitis
ADA	anti-drug antibodies
ADaM	Analysis data model
AE	adverse event
AESI	adverse event of special interest
ATC	Anatomical Therapeutic Chemical
AUC	area under the curve
BMI	body mass index
BSA	body surface area
DK	Denmark
DLQI	Dermatology Life Quality Index
EASI	Eczema Area and Severity Index
EASI50	At least 50% reduction in EASI score
EASI75	At least 75% reduction in EASI score
EASI90	At least 90% reduction in EASI score
ECG	electrocardiogram
EQ-5D-5L	EuroQoL 5-Dimension Health Questionnaire 5 Level
IIADC	
HADS	Hospital Anxiety and Depression Scale
HADS ICH	Hospital Anxiety and Depression Scale International Conference on Harmonisation
ICH	International Conference on Harmonisation
ICH IGA	International Conference on Harmonisation Investigator's Global Assessment
ICH IGA IMP	International Conference on Harmonisation Investigator's Global Assessment investigational medicinal product
ICH IGA IMP LOCF	International Conference on Harmonisation Investigator's Global Assessment investigational medicinal product Last observation carried forward
ICH IGA IMP LOCF MedDRA	International Conference on Harmonisation Investigator's Global Assessment investigational medicinal product Last observation carried forward Medical Dictionary for Regulatory Activities
ICH IGA IMP LOCF MedDRA nAB	International Conference on Harmonisation Investigator's Global Assessment investigational medicinal product Last observation carried forward Medical Dictionary for Regulatory Activities neutralising antibodies
ICH IGA IMP LOCF MedDRA nAB NRS	International Conference on Harmonisation Investigator's Global Assessment investigational medicinal product Last observation carried forward Medical Dictionary for Regulatory Activities neutralising antibodies numeric rating scale
ICH IGA IMP LOCF MedDRA nAB NRS PGI-B	International Conference on Harmonisation Investigator's Global Assessment investigational medicinal product Last observation carried forward Medical Dictionary for Regulatory Activities neutralising antibodies numeric rating scale Patient Global Impression of Bother
ICH IGA IMP LOCF MedDRA nAB NRS PGI-B PGI-S	International Conference on Harmonisation Investigator's Global Assessment investigational medicinal product Last observation carried forward Medical Dictionary for Regulatory Activities neutralising antibodies numeric rating scale Patient Global Impression of Bother Patient Global Impression of Severity
ICH IGA IMP LOCF MedDRA nAB NRS PGI-B PGI-S POEM	International Conference on Harmonisation Investigator's Global Assessment investigational medicinal product Last observation carried forward Medical Dictionary for Regulatory Activities neutralising antibodies numeric rating scale Patient Global Impression of Bother Patient Global Impression of Severity Patient Oriented Eczema Measure

Trial ID: LP0162-1325	Date: 20-May-2019	Version: 1.0
		Page 7 of 31

SAE	serious adverse event
SAP	Statistical Analysis Plan
SCORAD	Scoring Atopic Dermatitis
SCORAD50	At least 50% reduction in SCORAD score
SCORAD75	At least 75% reduction in SCORAD score
SF-36	36-Item Short Form Health Survey
SOC	System Organ Class
TCS	topical corticosteroid
TSQM	Treatment Satisfaction Questionnaire for Medication
WPAI-GH	Work Productivity and Activity Impairment – General Health

## 4 Introduction

The statistical analysis will be performed as outlined in the Clinical Trial Protocol including amendments.

This Statistical Analysis Plan is prepared before the unblinding of the trial and supplements the Clinical Trial Protocol, which otherwise describes the originally planned statistical analyses of all endpoints in an intended exhaustive manner. The Statistical Analysis Plan contains a more technical and detailed elaboration of some points related to the implementation of the statistical analyses already described in the Clinical Trial Protocol.

In addition, the Statistical Analysis Plan includes supplementary statistical analyses and aspects that are introduced after the latest protocol amendment, of which all are initiated as responses to FDA advices.

Supplementary analyses introduced according to LEO response to CCI letter dated

- ; Ref ID: CCI
  - 1. A tipping point analysis introduced as a sensitivity analysis number 3 for the primary estimand ('composite') for the primary endpoints (IGA 0/1 and EASI75) and the secondary endpoint (reduction of Pruritus NRS weekly average of at least 4 (yes/no)).
- 2. Analyses of a new tertiary estimand ('composite') for the continuous secondary confirmatory endpoints (change in SCORAD and change in DLQI). Analyses apply non-responder imputation for subjects who received rescue medication. A tipping point sensitivity analysis is included.

Other supplementary analyses introduced for consistency:

 The same analysis and tipping point sensitivity analysis as above implemented as a new tertiary ('composite') estimand for the two secondary additional endpoints 'Change from baseline to Week 16 in EASI score' and 'Change from baseline to Week 16 in Worst Daily Pruritus NRS (weekly average)'.

Modification of the US testing hierarchy introduced by LEO in Meeting Background Material for CCL meeting dated CCL representations; Ref ID: CCL and to address CCL letter dated CCL representations; Ref ID: CCL representation; Ref ID: CCL representa

4. A dedicated modified confirmatory testing hierarchy applied in the US submission. The originally specified testing hierarchy is kept for non-US submissions (e.g. to EMA and PMDA).

Trial ID: LP0162-1325	Date: 20-May-2019	Version: 1.0
		Page 9 of 31

The first aspect is addressed in section 6.6.2, the  $2^{nd}$  and  $3^{rd}$  are addressed in section 6.6.3 while the  $4^{th}$  aspect is presented in section 6.6.1.

# 5 Trial Analysis Sets

The trial analysis sets are defined in the protocol and the following modifications to the analysis sets for the initial- and maintenance periods are introduced.

All subjects randomised to initial treatment who were exposed to IMP are included in the full analysis set (FAS) and will be analysed for efficacy up to Week 16 (visit 12). For subjects not exposed to IMP, the decision to withdraw can't be biased by knowledge of the assigned treatment due to the blinding. This definition of the FAS implements the consideration mentioned in the protocol regarding special excluded cases with reference to ICH E9, Section 5.2.1.

The safety analysis set comprises all subjects randomised to initial treatment who were exposed to IMP. The protocol further specifies to exclude subjects from the safety analysis set for whom no post-baseline safety data are available. However, since all subjects receive the first dose of IMP in connection with the Week 0 visit and are subsequently monitored for immediate drug reactions, all exposed subjects are considered to have post-baseline safety data available and no such further exclusions will be made.

The maintenance analysis set is defined in the protocol as all subjects who receive tralokinumab in the initial treatment period and who are re-randomised to maintenance treatment. In addition to this, subjects who are not exposed to maintenance treatment will be excluded from the maintenance analysis set. This follows the same principle that leads to exclusion of unexposed subjects from the full analysis set and is in alignment with ICH E9.

The maintenance safety analysis set comprises all subjects who are re-randomised and receive at least one dose of maintenance treatment.

The open-label safety analysis set comprises all subjects who at any point in time enter the open-label treatment arm and receive at least one dose of open-label treatment.

For the follow-up period the safety follow-up analysis set will be used as the basis for evaluation of adverse events during the follow-up period. It comprises all subjects for whom date of last contact is after the date of exposure end, where exposure end is defined as the Week 52 visit (Week 68 visit for subjects enrolled in short-term extension) for subjects

Trial ID: LP0162-1325	Date: 20-May-2019	Version: 1.0
		Page 10 of 31

completing the treatment period, and otherwise the date of permanent discontinuation of IMP for subjects not completing the treatment period. See also section 6.8.2 for further details.

For analysis of efficacy subjects will be included 'as randomised'.

For analysis of safety, if a subject is mistakenly given an experimental therapy other than that to which they were randomized, they should be analyzed 'as-treated', thus included in the group according to the therapy actually received by the subject. The below rules will be applied.

Subjects who received at least one dose of tralokinumab during the initial treatment period will be analysed in the tralokinumab treatment group. Although this may dilute the AE rate in the tralokinumab treatment group slightly by including in the denominator subjects who only received one dose of active treatment, it will ensure that no significant drug reactions to tralokinumab will erroneously be assigned to placebo.

Subjects in the maintenance safety analysis set will be analysed as follows:

Week 16 Tralokinumab responders will be displayed in tables for the maintenance period according to actual treatment defined as:

- Tralokinumab Q2W if
  - subject was randomised to Tralokinumab Q2W and at least one dose of active treatment was administered, or
  - subject was randomised to placebo, but more than half of the administered doses contained active treatment.
- Tralokinumab Q4W if
  - subject was randomised to Tralokinumab Q4W and at least one dose of active treatment was administered, or
  - subject was randomised to placebo but at least one and at most half of the administered doses contained active treatment.
- Placebo if only placebo doses were administered

By assigning subjects randomised to placebo who got at least one active treatment to the Q4W arm a potential safety signal in the Q2W group is not deflated.

Week 16 placebo responders will be displayed in the "Week 16 placebo responders / Placebo" column in summary tables, regardless of actual treatment received. Any deviations from the

Trial ID: LP0162-1325	Date: 20-May-2019	Version: 1.0
		Page 11 of 31

planned treatment regimen (i.e. if any active doses are given) will be described as protocol deviations.

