- Placebo (4 mL) at baseline, then placebo (2 mL) Q2W.

Maintenance treatment period (Week 16 to Week 52)

Subjects achieving a clinical response at Week 16 will continue into maintenance treatment that will continue until Week 52.

Clinical response is defined as IGA of 0 or 1, or at least 75% reduction in EASI score from baseline (EASI75).

Subjects randomised to tralokinumab in the initial treatment period will be re-randomised 2:2:1 to one of the following Q2W maintenance regimens stratified by region and IGA response at Week 16 (IGA 0/1 or IGA >1):

- Tralokinumab 300 mg (2 mL) ('tralokinumab Q2W').
- Alternating dose administrations tralokinumab 300 mg (2 mL) and placebo (2 mL) ('tralokinumab Q4W').
- Placebo (2 mL).

Subjects randomised to placebo in the initial treatment period who achieve a clinical response at Week 16, defined by IGA of 0 or 1, or EASI75 will continue to receive placebo Q2W in the maintenance treatment period.

Transfer to open-label treatment

Subjects will be transferred from maintenance treatment to open-label treatment (tralokinumab 300 mg Q2W with optional use of TCS) if they meet the criteria listed below. Transfer to open-label may occur at any visit while the subject is in the maintenance treatment period but no earlier than Week 22.

Subjects with IGA=0 at Week 16:

• IGA of at least 2 and not achieving EASI75 over at least a 4-week period (i.e., over 3 consecutive visits).

Subjects with IGA=1 at Week 16:

• IGA of at least 3 and not achieving EASI75 over at least a 4-week period (i.e., over 3 consecutive visits).

Subjects with IGA >1 at Week 16:

• Not achieving EASI75 over at least a 4-week period (i.e., over 3 consecutive visits).

Subjects who are transferred to open-label treatment will continue their scheduled visit sequence.

Open-label treatment (Week 16 to Week 52)

Any subject that does not achieve the protocol defined clinical response at Week 16 will be treated with open-label tralokinumab 300 mg Q2W with optional use of TCS. The open-label treatment will extend to Week 52.

For selected countries

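### SAP section 5 keeps Week 16 placebo responders in a placebo safety column whatever they receive in maintenance, an unexplained exception to its own as-treated rule

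*SAP*

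**What the plan says.** SAP section 5 opens its safety rules with a general principle for subjects given a therapy other than the one they were randomised to: "they should be analyzed 'as-treated', thus included in the group according to the therapy actually received by the subject". Specific rules follow.

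- **Initial period.** "Subjects who received at least one dose of tralokinumab during the initial treatment period will be analysed in the tralokinumab treatment group". The SAP accepts some dilution of the tralokinumab rate because "it will ensure that no significant drug reactions to tralokinumab will erroneously be assigned to placebo".
- **Maintenance, Week 16 tralokinumab responders.** Display follows actual treatment. A subject re-randomised to placebo who received any active dose goes to Q4W or Q2W, depending on the share of active doses. The last category is "Placebo if only placebo doses were administered".
- **Maintenance, Week 16 placebo responders.** These subjects are shown in their own placebo "column in summary tables, regardless of actual treatment received". Departures from the "planned treatment regimen (i.e. if any active doses are given) will be described as protocol deviations".

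Protocol section 7.1 says that these placebo responders "will continue to receive placebo Q2W in the maintenance treatment period". SAP section 6.8.8, Table 6, gives them the fourth maintenance column, after the three columns for tralokinumab responders.

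**The concern.** The SAP states an as-treated principle, applies it to two groups, and reverses it for a third without explanation. Placebo was the only treatment that Week 16 placebo responders were ever randomised to, so an active dose during their maintenance period is the kind of error the principle addresses.

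At stake is where an event appears. If such a subject has a reaction after an erroneous tralokinumab dose, the maintenance table counts it in a column labelled placebo. A placebo responder dosed as planned has had no tralokinumab before that point, so the dose would be a first exposure. Protocol section 5.5 lists hypersensitivity among the potential risks, and section 9.2 requires observation after the first three dosing visits of the initial and open-label periods. Describing the dose as a protocol deviation discloses it, but does not move or mark the event in the adverse event table.

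**Working it through.** The plan gives no figure on this point, so the check is first a comparison of rules and then a bound on size.

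**1. The rules side by side** (SAP section 5), for a subject assigned to placebo who receives at least one active dose:

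| Group | Shown under | Reason given |
|---|---|---|
| General safety principle | Therapy received | The principle itself |
| Initial period, placebo arm | Tralokinumab | Keep drug reactions out of placebo |
| Maintenance, tralokinumab responder re-randomised to placebo | Q4W if at most half of doses were active, Q2W if more | Avoid deflating a signal in Q2W |
| Maintenance, Week 16 placebo responder | Placebo | None |

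Only the last row departs from the principle.

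**2. Which events are exposed.** An active dose before Week 16 falls under the initial-period rule for the initial-period tables. Events from the first open-label dose onward go to the open-label period (SAP section 6.7.1 and section 6.8.2, Table 4). What remains is an event after an erroneous active dose during maintenance, before any open-label transfer.

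**3. Which totals are affected.** SAP section 6.7.1 sorts the maintenance tables by the sum of Q2W and Q4W. A misdosed placebo responder is in neither column, so the event is outside that sum. The same section mentions a tralokinumab total for the entire treatment period but does not say how it is built. Exclusion from that total is therefore not shown.

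**4. Size of the column.** Inputs from Protocol section 12.1: 195 placebo subjects, with assumed Week 16 placebo response of 15% for EASI75 and 10% for IGA 0/1. Entry to maintenance requires either one (Protocol section 7.1).

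- Lower bound, every IGA 0/1 responder also an EASI75 responder: 195 × 0.15 = 29.25, about 29.
- Upper bound, no overlap: 195 × (0.15 + 0.10) = 48.75, about 49.

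**5. Effect of one case.** For one misdosed subject whose event is not otherwise counted in that row of the table:

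- 1/29 = 3.4 percentage points.
- 1/49 = 2.0 percentage points.

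**The case against.** The strongest reply is that this is a deliberate special case that fits the table structure. The maintenance columns are defined by Week 16 population as well as by drug, and no existing column suits a placebo responder who received active drug. Moving that subject into a Week 16 Tralokinumab responders column would mislabel someone who was never part of the 2:2:1 re-randomisation. That stands, and it rules out one possible remedy. It does not explain why the subject should be shown as placebo, and the SAP offers no explanation.

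The error would also be visible elsewhere. Protocol section 11.5.3 requires a medication error to be recorded on the adverse event form, with resulting events on a separate line. Section 12.3.7.1 provides listings of all adverse events and a narrative for each serious one. This also stands, but none of it changes the count in the placebo column.

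Three stronger readings are tempting and are not supported.

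- **That the drug-versus-placebo safety comparison is biased.** The column is separate from re-randomised placebo (SAP section 6.8.8, Table 6), so Q2W and Q4W are still compared with an uncontaminated group. Protocol section 12.3.7.1 specifies significance tests on adverse events only for the initial period.
- **That the SAP breaks its stated aim of keeping drug reactions out of placebo.** That aim is given for the initial period only. The reason given for re-randomised subjects is a different one. The conflict is with the general as-treated principle.
- **That such events drop out of every tralokinumab total.** This is shown only for the maintenance sum of Q2W and Q4W. For full-trial exposure, Protocol section 12.3.3.1 counts days on tralokinumab whatever the treatment group.

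**Conclusion.** The inconsistency is real but minor. A written rule, not a missing detail, places an event after an erroneous active dose in a column labelled placebo, against the principle stated just before it.

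The size estimate of 2.0 to 3.4 points per case rests on the protocol's planned placebo arm and assumed response rates, on all such responders entering maintenance, and on the event not already being counted for that subject. The documents do not say how many placebo responders were misdosed, so the realised effect may be nil. Efficacy, type 1 error and sample size are not involved.

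**What to change.** In SAP section 5, replace the rule for Week 16 placebo responders with an as-treated rule covering the whole maintenance period. A placebo responder with at least one active maintenance dose would be shown in a separate column, for example 'Week 16 placebo responders: received active in error', and not in a Week 16 Tralokinumab responders column. Flag these subjects' events and count them in any overall tralokinumab total.

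Allocating the whole subject for the period matches the other rules in section 5. Splitting a subject at the first active dose would be a different rule and would need person-time or dual denominators.

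The cost is a reworded sentence, a treatment-received flag, an added label in Table 6 and an extra column that will probably be nearly empty. Including these subjects dilutes the tralokinumab total slightly, a trade the SAP already accepts in the initial period. If the exception is kept, the SAP should at least state the reason and footnote or list the adverse events of any placebo responder who received an active dose.
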